5 INTERVENTION

All participants attend introductory lecture, where a urologist informs them about adverse effects of ADT and positive effects of exercise during ADT, exercise instructor gives advice for training both at home and in the gym and nutritional therapist tells about nutrition to overcome adverse effects of ADT and support training.

After the introductory lecture the participants are randomized 1:1 to either the supervised or non-supervised exercise group (Figure). Men in the supervised group participate in progressive group exercise sessions twice a week for total of 12 weeks at the Varala sports academy in Tampere, Finland. Each exercise session includes both aerobic and resistance training targeting all major muscle groups (Additional document I, exercise program). The non-supervised group will exercise independently for 12 weeks according to the instructions given at the introductory lecture. The first control visit will be after this first period of 12 weeks of exercise.

After the first follow-up visit both groups will continue non-supervised exercise for 12 weeks, after which the second control visit will be arranged. Special focus on the second control visit is to see how many in each group has been able to carry on active exercising, i.e. has the intervention promoted long-term change in exercise activity.

Both study groups will be given Polar wrist activity monitors to be used 24 h/day for the entire course of the study.

All participants are asked to fill validated quality of life surveys EORTC QLQC-30 (overall quality of life) and EORTC QLQC-PR25 (prostate cancer-specific quality of life) at baseline and again at 1st and 2nd control visits. Plasma lipid and glucose parameters, blood pressure and body composition will be measured at each of these visits.

At each visit a separate blood sample is taken and stored for future measurement of biomarkers associated with prostate cancer progression, glucose and lipid metabolism and effects of exercise.

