3 STUDY SETTING

This is a randomized, controlled clinical trial. The study aims to recruit 40 men on ADT for prostate cancer. This will be a pilot study to estimate effect sizes in Finnish population to inform further larger trial. For this reason the sample size will be smaller compared to previous studies on the topic (10,11) and no power calculation is performed yet.

Figure: Study flow chart

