6 QUALITATIVE EVALUATION OF SUBJECTIVE CAPABILITIES AND QUALITY OF LIFE

On each visit a qualitative evaluation will be performed based on individual- and group interviews to evaluate how men find ADT and exercise affecting their quality of life and how they perceive the intervention as a means to increase their physical activity. On the interviews information will be collected on:

1. How men on ADT perceive their quality of life and what is their subjective definition of quality of life?
 - What kind of side-effects they have had from ADT, how they cope with them in everyday life and how cancer, ADT and ADT side-effects have affected their quality of life?
 - What role exercise has had in their lives before prostate cancer and after it, and how the amount of exercise is tied to their perceived quality of life?

2. What kind of opportunities and obstacles of exercise the participants find in their lives?
 - How men in the supervised exercise group think the intervention will affect their exercise activity in the future? Can supervised exercise help to overcome obstacles for exercising?
 - How men in the non-supervised exercise group cope with obstacles for exercise?

Baseline interview, before the study randomization: A group of 10 men are interviewed before randomization to the exercise groups. The goal is to find how participants expect the intervention to affect their activity and quality of life before they know in which group they will participate.

Second interview at the first control visit: Men in the supervised exercise group are interviewed about the role of their group and supervision on their exercise activity and perceived quality of life. Non-supervised group is interviewed how they have managed to follow the given exercise program and how it has affected their quality of life. All men are asked how they think their exercise habits would have differed had they been randomized to the other intervention group. Additionally their views about how they will be able to carry on exercising will be asked.

Third interview at the second control visit: The questions will evaluate how men have carried on with the exercise; have they been able to increase it or has it rather decreased; have the men found that the exercise intervention has affected their quality of life.

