7 STUDY OUTCOMES AND STATISTICAL ANALYSIS

Primary outcomes:

- Daily total activity, measured during the entire course of study with wrist activity monitor in metabolic equivalents of task (MET) units
- Fasting plasma cholesterol, LDL, HDL and triglycerides, measured at baseline and again at the 1st and 2nd control visits
- Fasting plasma glucose and glycated haemoglobin (HbA1C), measured at baseline and again at the 1st and 2nd control visits
- Overall quality of life and prostate cancer-specific quality of life, measured with validated Finnish versions of EORTC QLQ-C30 v.3.0 ja EORTC QLQ-PR25 at baseline and at each control visit

Secondary outcomes:

- Change in daily activity after the end of supervised group exercise intervention; difference compared to the non-supervised group. Measured with wrist activity monitor in MET units
- Body mass composition, bioimpedance-based measurement of lean body mass, fat mass and skeletal mass as percentage of total body mass measured with TANITA MC-780 device

- Blood pressure level, measured at baseline and each control visit
- Subjective effect of exercise on quality of life and perceived adverse effects of ADT, as based on qualitative interviews

Long-term follow-up

The participants are followed via patient files and national health care registries. Outcomes to be followed are:

- Time from baseline to castration resistance (progression of prostate cancer despite ADT as evidenced by constantly rising PSA or radiological disease progression)
- Bone fractures
- Diagnosis of memory impairment
- Diagnosis of diabetes mellitus
- Diagnosis of cardiovascular disease
- Prostate cancer death
- Death due to any cause

Statistical analysis

All comparisons are done between the supervised and non-supervised exercise arms. Medians of daily activity (in MET units) and quantitative quality of life (as points from the EORTC surveys) at baseline and at each control visit are compared with either Mann-Whitney U-test or Student's t-test depending on normality of the data distribution. Difference in medians of plasma lipid parameters and glucose parameters are analyzed similarly.

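### Only the supervised arm trains in groups, yet the post-baseline tests assume independent men; if outcomes correlate within training groups, precision is overstated

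*Combined protocol and SAP*

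**What the plan says.** Section 3 (Study setting) sets the size and purpose: "The study aims to recruit 40 men on ADT for prostate cancer", and "This will be a pilot study to estimate effect sizes in Finnish population to inform further larger trial". It adds that "no power calculation is performed yet".

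Section 5 (Intervention) randomises individual men: "the participants are randomized 1:1 to either the supervised or non-supervised exercise group". Delivery then differs by arm. For the supervised arm: "Men in the supervised group participate in progressive group exercise sessions twice a week for total of 12 weeks". For the comparator: "The non-supervised group will exercise independently for 12 weeks according to the instructions given at the introductory lecture". After the first control visit, both arms train without supervision for a further 12 weeks.

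Section 7 (Statistical analysis) says that activity and quality of life "at baseline and at each control visit are compared with either Mann-Whitney U-test or Student's t-test", with the choice depending on normality. Lipids and glucose are handled the same way. There is no cluster term, robust standard error or design effect. The number and size of training groups, whether membership is fixed, and the number of instructors are not stated.

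Section 6 (Qualitative evaluation) makes the group an interview topic: "Men in the supervised exercise group are interviewed about the role of their group and supervision on their exercise activity".

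**The concern.** This is a partially nested design: men are randomised individually, but those in one arm then share sessions, and possibly an instructor and peers, for 12 weeks. If some training groups do better than others, outcomes of men in the same group are correlated, and 20 supervised men carry less information than 20 independent men. The planned tests do not allow for this.

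What is at stake is mainly the pilot's output. Its purpose is to supply effect sizes for a larger trial. Overstated precision would pass into that trial's planning. If group membership is not recorded, the pilot also cannot say anything about the clustering that a larger trial with group sessions would have to allow for.

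**Working it through.** **Inputs from the documents.** 40 men, 1:1, so about 20 per arm; group delivery in the supervised arm only; t-test or Mann-Whitney between arms.

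**Inputs assumed, because the documents do not give them.** Two-sided 5% level; equal total variance in both arms; m men per training group, with m = 5, 10 or 20 (four, two or one groups); ICC of 0.01, 0.05 or 0.10.

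**Plan's own figure.** The target of 40 has no power calculation behind it, so there is nothing to reproduce. For reference, 20 independent men per arm give 80% power for a standardised difference of (1.96 + 0.84) × √(2/20) = 0.89.

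**Formulas.**
- Supervised-arm design effect: DE = 1 + (m − 1) × ICC.
- Variance of the arm difference: σ² × (DE/20 + 1/20).
- True SE divided by nominal SE: √((DE + 1)/2).
- Type I error of the nominal 5% test: 2 × (1 − Φ(1.96 / SE ratio)).

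**One case in full** (m = 10, ICC 0.05). DE = 1 + 9 × 0.05 = 1.45. SE ratio = √(2.45/2) = 1.107. 1.96/1.107 = 1.77, so the type I error is 7.7%. Effective supervised sample = 20/1.45 = 13.8 men.

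**All cases.** The last two columns are simulated rejection rates (40,000 runs for the t-test, 20,000 for Mann-Whitney).

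| Groups | ICC | DE | SE ratio | Type I, formula | t-test | Mann-Whitney |
|---|---|---|---|---|---|---|
| 4 of 5 | 0.01 | 1.04 | 1.01 | 5.2% | 5.3% | 5.2% |
| 4 of 5 | 0.05 | 1.20 | 1.05 | 6.2% | 6.2% | 5.9% |
| 4 of 5 | 0.10 | 1.40 | 1.10 | 7.4% | 7.3% | 7.0% |
| 2 of 10 | 0.01 | 1.09 | 1.02 | 5.5% | 5.6% | 5.3% |
| 2 of 10 | 0.05 | 1.45 | 1.11 | 7.7% | 7.8% | 7.6% |
| 2 of 10 | 0.10 | 1.90 | 1.20 | 10.4% | 10.7% | 10.3% |
| 1 of 20 | 0.01 | 1.19 | 1.05 | 6.1% | 6.3% | 6.0% |
| 1 of 20 | 0.05 | 1.95 | 1.21 | 10.7% | 10.9% | 10.4% |
| 1 of 20 | 0.10 | 2.90 | 1.40 | 16.0% | 17.0% | 16.3% |

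At ICC 0, DE = 1 and the tests keep their nominal level. At ICC 0.05 the difference detectable with 80% power moves from 0.89 to 0.93, 0.98 and 1.08 SD for groups of 5, 10 and 20.

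**Does a mixed model help with three or four groups?** Take ICC 0.05 and approximate the partially nested analysis by Satterthwaite degrees of freedom on the cluster means: df = (DE + 1)² / (DE²/(k − 1) + 1/19), where k is the number of groups.
- k = 4, DE = 1.20: df = 4.84/(0.480 + 0.053) = 9.1. The critical value is 2.26, against 2.02 on 38 df. Interval width changes by 1.05 × 2.26/2.02 = 1.17.
- k = 3 (about 6.7 men each), DE = 1.28: df is about 6.0. The critical value is 2.45, and width changes by 1.07 × 2.45/2.02, about 1.30 (rounded).

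The model would widen intervals by about 17-30% to correct an SE understated by about 5-7%.

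**Does the simple widening work?** Multiplying the supervised arm's variance term by DE brought the simulated type I error back to about 5-6% in all nine settings when the assumed ICC equalled the true one.

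**The case against.** **The claim is conditional.** It is tempting to say that the standard errors are too small and the false-positive rate exceeds 5%. The documents do not support that as a fact. It needs a positive ICC, and neither the ICC nor the group sizes are given. With groups of 5 and ICC 0.01 the effect is negligible. This stands.

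**Not every primary test is involved.** A reader might infer that all of them are. Baseline comparisons precede the sessions and are unaffected. By the second control visit both arms have had 12 weeks of unsupervised training, so a session-group effect may have faded. This stands.

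**Section 6 can be over-read.** Asking men about the role of their group shows only that the group may matter. A benefit of training with peers that all supervised men share is part of the intervention effect; correlation arises only if some groups do better than others. The word group there may also mean the trial arm. This stands.

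**The documents also point the other way.** Section 8.1 speaks of tailoring to individual performance level, and Additional document I is a per-man sheet with his own settings and loads. That gives less reason to expect a high ICC, particularly for lipids and HbA1c. This stands, and is why activity and quality of life are the outcomes of most concern.

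**The null matters.** If supervised training affects no one, shared sessions cannot create correlation, and the tests hold their level. The inflation applies when group effects vary around an average of zero. That limits the type I error statement. It does not remove the precision problem when the effect estimate is to be carried over to new groups in a larger trial.

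**With one group, the widening only returns the assumed ICC.** That is so: the group is then fully confounded with the arm, and no analysis can separate them. The widened interval is a sensitivity display, not an estimate.

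**Conclusion.** The point holds in conditional form. Group delivery in one arm, tests that assume independence, and no allowance for clustering are all plain in the documents. If outcomes correlate within training groups, the nominal standard errors of the post-baseline comparisons are too small by a factor of 1.01 to 1.40 over the range examined. Type I error would then be about 5-7% (four groups of 5), 5-11% (two groups of 10) or 6-17% (one group of 20). These figures rest on 20 men per arm, equal variances, a two-sided 5% level and ICC 0.01 to 0.10, of which only the arm size follows from the documents.

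The issue is one of precision, not a systematic shift in the estimate, except that a single training group could not be distinguished from supervision itself. The documents do not support the further inference that a mixed model must replace the planned tests: with so few groups it can cost more precision than the problem it corrects. For a 40-man pilot this is a worthwhile, inexpensive improvement rather than a flaw that undermines the trial.

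**What to change.** 1. Record each supervised man's training group and instructor while the sessions run, and state the number and size of groups and whether membership is fixed.
2. Keep the planned simple comparison as the main analysis. Do not require a mixed model.
3. Beside it, as a sensitivity analysis, report each post-baseline arm difference with an interval whose standard error is √(DE × s₁²/n₁ + s₀²/n₀). Here DE = 1 + (m − 1) × ICC, ICC runs from 0.01 to 0.10, m is the actual group size, and subscript 1 is the supervised arm. Section 7 names tests only, so the interval has to be added.
4. If there is only one training group, state that its effect cannot be separated from that of supervision.
5. Carry this ICC range, or an observed ICC with its wide uncertainty, into the larger trial's sample size.

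Cost: one recorded item per supervised man (group and instructor) and a paragraph of analysis text. No extra patients or visits. The stated precision becomes slightly less favourable.

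### Daily activity is to be compared between arms at baseline, but the plan does not say when monitors are issued or which days form that baseline, and it uses no baseline covariate

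*Combined protocol and SAP*

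**What the plan says.** Section 5 (Intervention) begins with an introductory lecture for everyone, at which an "exercise instructor gives advice for training both at home and in the gym". Allocation follows: "After the introductory lecture the participants are randomized 1:1 to either the supervised or non-supervised exercise group". The section then describes the 12-week exercise period, the first control visit, a further 12 weeks and the second control visit. Only after that does it mention the monitors: "Both study groups will be given Polar wrist activity monitors to be used 24 h/day for the entire course of the study". It gives no day or visit for the hand-out.

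Section 7 (Study outcomes and statistical analysis) lists activity as a primary outcome: "Daily total activity, measured during the entire course of study with wrist activity monitor in metabolic equivalents of task (MET) units". The laboratory outcomes are worded differently, with named time points: "Fasting plasma cholesterol, LDL, HDL and triglycerides, measured at baseline and again at the 1st and 2nd control visits". The analysis paragraph nevertheless treats activity as having a baseline value. It names "Medians of daily activity (in MET units) and quantitative quality of life (as points from the EORTC surveys) at baseline and at each control visit" as the quantities to be compared between arms, by Mann-Whitney or t-test. No change score or baseline adjustment is stated for activity.

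The study flow chart cited in Sections 3 and 5 is not visible in the text available for this review.

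**The concern.** A blood sample or questionnaire can be completed at one visit. Usual daily activity cannot: it needs several days of wear. A pre-intervention activity baseline therefore exists only if wear days before allocation are planned, and the text describes none. The monitors are described as going to the study groups, and groups exist only after randomisation. If that wording reflects practice, the earliest recorded days come after allocation and may include assigned exercise.

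Three things would then be at stake:

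- **The planned baseline comparison.** It could show an arm difference that is early treatment effect and not chance imbalance.
- **The hypothesis in Section 2.** It concerns a greater increase in activity under supervision. An increase needs a starting level that the intervention has not touched.
- **The pilot's purpose in Section 3.** The trial is meant to estimate effect sizes for a larger trial. Effects or SDs of change measured from a contaminated starting point would mislead that design.

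Separately, a 40-man trial gains from a clean baseline used as a covariate, and the stated tests do not use one. Pre-intervention activity that was not recorded cannot be recovered later.

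**Working it through.** **Step 1. Is a baseline window defined?** Section 7 needs a baseline activity value, yet its outcome definition for activity gives only the whole study as the measurement period. Section 5 gives no hand-out time. The only procedure explicitly timed before randomisation is the interview of 10 men in Section 6. So the window is undefined in the text. Issue after allocation is a fair inference, but it is not stated.

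**Step 2. Inputs for sizing.** The plan gives no power calculation, effect size or SD, so there is no figure to reproduce.

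- From the documents: 40 men at 1:1, so n = 40/2 = 20 per arm (no dropout allowed for).
- Assumed: two-sided 5% level; true arm difference D = 0.5 SD at follow-up; baseline-to-follow-up correlation ρ = 0.5 to 0.7; equal variances at both times.
- Assumed: f, the share of D already present in the baseline window, at 0, 0.25 or 0.5.

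**Step 3. Formulas.** Power ≈ Φ(difference / (s·√(2/n)) − 1.96), with √(2/20) = 0.316.

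- Follow-up only, as planned: difference D, s = 1.
- Change from baseline: difference D(1 − f), s = √(2(1 − ρ)).
- Baseline as covariate (ANCOVA): difference D(1 − fρ), s = √(1 − ρ²).
- Baseline comparison: spurious arm difference fD.

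**Step 4. Precision available from a clean baseline (f = 0).**

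- Unadjusted: 0.5/0.316 = 1.581; 1.581 − 1.96 = −0.379; power 35%.
- Covariate, ρ = 0.5: s = √0.75 = 0.866; 0.5/(0.866 × 0.316) = 1.826; power 45%.
- Covariate, ρ = 0.7: s = √0.51 = 0.714; 0.5/(0.714 × 0.316) = 2.214; power 60%.

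In sample-size terms, the clean covariate makes 20 men per arm worth about 20/0.75 = 27 at ρ = 0.5 and 20/0.51 = 39 at ρ = 0.7.

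**Step 5. Effect of a contaminated baseline.**

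| Analysis | ρ | f = 0: difference, power | f = 0.25 | f = 0.5 |
|---|---|---|---|---|
| Follow-up only (planned) | any | 0.50, 35% | 0.50, 35% | 0.50, 35% |
| Change from baseline | 0.5 | 0.50, 35% | 0.375, 22% | 0.25, 12% |
| Change from baseline | 0.7 | 0.50, 53% | 0.375, 33% | 0.25, 17% |
| Covariate | 0.5 | 0.50, 45% | 0.44, 36% | 0.375, 28% |
| Covariate | 0.7 | 0.50, 60% | 0.41, 45% | 0.325, 30% |

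The baseline comparison itself would show 0.25 × 0.5 = 0.125 SD at f = 0.25 and 0.5 × 0.5 = 0.25 SD at f = 0.5.

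The planned analysis at the control visits (first row) does not move. The loss falls on change and adjusted estimates. These are normal-theory figures for means. They are slightly optimistic at this sample size and only indicative for a rank test.

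**The case against.** The strongest reply is that the plan never says the monitors are issued after randomisation. Section 5 is not chronological: the monitor sentence follows the second control visit, and the next paragraph returns to baseline questionnaires and blood tests. Wear over the whole study could include days before allocation, the flow chart might show this, and Section 6 uses the word baseline for a time before randomisation. All of this stands. A reader might infer that baseline activity does contain the intervention; the documents support only that it may.

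A reader might also infer that the primary comparison of activity is biased, even to the point of losing the whole effect. If the full effect appeared in week 1 and week 1 served as baseline, a change score would show none of it, and an adjusted model with an assumed slope of 0.6 to 0.8 would show 40% to 20%. The documents do not support applying those figures here. The plan states neither a change score nor an adjusted model for activity, Section 5 describes the group sessions as progressive, and no interval from randomisation to first session is given.

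Two further limits stand. The lecture is common to both arms and precedes allocation, so it can shift the level in both but cannot by itself create an arm difference. The secondary outcome on activity after the supervised period need not refer to baseline at all.

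The objection does not supply a definition of baseline activity, and it does not recover the precision that a covariate would give.

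**Conclusion.** The point holds in conditional form. A planned comparison of a primary outcome uses a baseline that the text leaves undefined, and the wording and order of Section 5 make issue after allocation plausible. If that happens, the between-arm comparisons at the control visits remain valid. The baseline comparison, any change or baseline-adjusted estimate, and the effect sizes or SDs of change taken to the larger trial would be distorted. With a quarter to a half of a 0.5 SD effect already present, a change score would recover 75% to 50% of the effect.

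Independently of hand-out timing, the stated tests forgo precision: about 35% power against about 45% to 60%. The effect size, correlations and contaminated share are all assumptions, because the documents give none of them.

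This is a cheap improvement worth making before recruitment. It is not a flaw that invalidates the planned analysis.

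**What to change.** - State in Section 5 that monitors are issued at recruitment and that about 7 valid days of wear, with a stated rule for a valid day, are completed before randomisation. If each arm's increase from usual activity is also to be reported, complete those days before the lecture. For the between-arm comparison alone, completion before randomisation is enough.
- In Section 7, define baseline activity as the mean of those days.
- Replace the unadjusted activity tests by between-arm comparisons for weeks 1-12 and weeks 13-24 with baseline activity as a covariate. If the data are clearly skewed, use a transformed or rank-based form.

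The cost is about one week of lead-in and a few sentences of text, using monitors that the trial already supplies. If the flow chart already shows a wear window before randomisation, only the definition and the covariate need adding. If no such window is feasible, the baseline activity comparison should be dropped and the plan should say so.
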